## 4.3 Inclusion Criteria

The following are requirements for entry into the study:

- 1. patient was aged  $\geq$  5 years to  $\leq$  17 years of age at the time of informed consent for the preceding study, 191622-120
- 2. patient has participated in Study 191622-120 and fulfilled that study's exit criteria (completed the qualification for retreatment/exit visit or the week 48/exit visit if they never qualified for retreatment)

[figure not shown]

5. patient must be regularly using CIC to empty the bladder (CIC can be performed by either the patient or the parent/caregiver)

[figure not shown]

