# 7.4 Safety Analyses

All safety analyses will be conducted on the BOTOX-treated population. Safety variables are adverse events, serious adverse events, physical examination, vital signs, laboratory tests (urinalysis, hematology and clinical chemistry), renal function, kidney and bladder ultrasound, concomitant medications, concurrent procedures, and pregnancy test for females who are postmenarche.

Medical Dictionary for Regulatory Activities (MedDRA) nomenclature will be used to code adverse events. For each adverse event reported, the number and percent of patients will be tabulated based on the preferred term. The tables will be generated by relationship to treatment as well as by primary system organ class and severity.

Data will be presented by BOTOX treatment cycle and grouped according to the actual dose received at that treatment cycle (grouped to the nearest dose group [50, 100, or 200 U BOTOX]), as well as by an overall BOTOX group (ie, regardless of dose).

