# 9.1.2 Definition of Adverse Events of Urinary Tract Infection and Urinary Retention

Study-specific definitions for the adverse events of UTI and urinary retention are provided below.

Adverse Event of Urinary Tract Infection

An adverse event of UTI is defined as being a symptomatic UTI that requires treatment in the opinion of the investigator.

Note: If urinalysis/culture results are reported which, in the opinion of the investigator, are considered clinically significant but do not fulfill the above definition of a UTI, the findings should be recorded as adverse events (eg., bacteriuria, leukocyturia).

Adverse Event of Urinary Retention

Urinary retention should only be reported in patients who had the ability to spontaneously void between catheterizations prior to study treatment. It is defined in these patients as the inability to spontaneously void for at least 24 hours, which is not in conjunction with the patient experiencing constipation.

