2.1 Analysis Populations

One analysis population will be used in the statistical analysis of this study namely, the BOTOX-treated population.

BOTOX-treated population will include all patients that enrolled into study 191622-121 after receiving BOTOX injection in study 191622-120. A patient is considered to have enrolled in study 191622-121 if in study191622-120, in the extension eCRF page, it is marked that a patient will continue into study 191622-121.

Actual Dose Administered	BOTOX Treatment Group
<75 U	50 U BOTOX
75 U ≥ and < 150 U	100 U BOTOX
≥ 150 U	200 U BOTOX

Table 1 BOTOX Treatment Groups Based on Actual Dose Administered

For cycle based analysis, since the patient's dose can be increased in a blinded fashion from one cycle to the next, the analysis will be based on actual treatment received during that cycle and will be assigned to the nearest dose group per Table 1 above. As a result of either the 6 U/kg weight cap or site error, patients may not receive the dose assigned per the IWRS (interactive web response system).

Patients will be assigned to actual treatment groups for analysis purposes as follows:

- 1. If the "incorrect unit dose administered" is populated in the eCRF, this dose will be used and adjusted per Table 1 above.
- 2. If the "incorrect unit dose administered" is not populated in the eCRF, then the randomized dose per IWRS (ie, 50U, 100U, or 200U) and the patient's weight at the qualification for retreatment visit will be utilized to determine the actual dose administered as described in section 12.1 of the study protocol. The dose administered will then be adjusted per Table 1 above.

For analysis that is not cycle based (e.g. baseline and disease characteristics), the summary will be by the overall BOTOX -treated population and by what the BOTOX- treated patients received in Cycle 1, which also coincides with the Study 191622-120 safety treatment groups. In this document these treatment groups will be referred to as Cycle 1 treatment groups.

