2.3.1 Data Conventions Limited to Diary data

- Study baseline diary information refers to the baseline information collected at the start of study 191622-120 (see Section 2.2).
- For study baseline and post-treatment visits, analyses will be based on the diary data collected over two consecutive days. For each day, the bladder diary will be used to collect date, time, and type of voiding episode (urinary incontinence, catheterization, or voluntary void) for each daytime episode (time between waking up to start the day and going to bed to sleep for the night). Furthermore, volume of urine on catheterization at morning wakening, the time the patient went to bed to sleep at night and the time the patient woke up in the morning and presence/absence of night time urinary incontinence will be collected for each diary day.

- The visit windows defined in Section 2.2 will be used to derive a patient's diary parameters for each visit.
- A valid diary day is defined as a day where there are one or more urinary episodes of any type (incontinence, catheterization, or voluntary void) during the daytime collection period. In the case of patients who provide just one valid diary day within a visit window, the 2-day frequency of daytime urinary incontinence will be prorated with the value from the valid diary day.
- If there are no valid diary days within the window, the 2-day diary data will be set as missing for the visit.
- For baseline and post-treatment visits, the 2-day diary will be determined based on the following algorithm:
 - 1) Apply visit windows defined in Section 2.2, which are based on days from the date of study drug injection.
 - 2) Determine the time of the first daytime urinary episode that is within the visit window (in the example below, 8:30 am on May 4). Count forward two consecutive daytime diary collection days. Note: the second daytime period should end within the window, i.e., prior to or on the last day specified in the window definition; otherwise, the nighttime or daytime data will not be used for the corresponding window. For baseline diary data, any urinary episode collected up to the time of injection will be counted towards the baseline diary data.

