6.2 Adverse Events

Adverse events (AEs) will be coded by system organ class and preferred term using the Medical Dictionary for Regulatory Activities (MedDRA).

Pre-treatment AEs are AEs that have start date on or after the signing of consent form and prior to the first BOTOX injection.

An AE will be considered a cycle 1 treatment-emergent adverse event (TEAE) if it fulfills one of the conditions below:

• the start date of the AE is on or after the 1st BOTOX injection and prior to the date of the 2nd BOTOX injection

• the AE started before the 1st BOTOX injection and increased in severity or became serious during the cycle (from date of 1st BOTOX injection to the day before the 2nd injection).

For subsequent cycles (cycle's number > 1) an AE is considered a TEAE in the current cycle if it fulfills one of the conditions listed below.

- the AE start date is within the cycle i.e., it is on or after the date of the cycle injection and prior to the date of the next injection
- the AE has increased in severity or became serious during the current cycle

The incidences of TEAEs will be summarized by BOTOX treatment cycle.

The number and percentage of patients reporting TEAE in each treatment group will be tabulated by descending percentage in any group, by system organ class and preferred term, and further categorized by severity and causal relationship to the study drug and study drug injection procedure. If more than 1 AE is coded to the same patient, the patient will be counted only once for that preferred term using the greatest severity for the summarization by severity and causal relationship.

The number and percentage of patients who have treatment-emergent serious adverse events (TESAE) will be summarized by system organ class, preferred term and treatment group. Similar summary will be presented for patients with TEAE leading to discontinuation from the study. In addition, separate patient listings will be generated for deaths, SAEs, and TEAEs leading to study discontinuation.

In addition, the incidence of TEAEs, SAEs, study drug/study injection procedure related TEAEs, deaths and TEAEs leading to study discontinuation will be reported for the overall study period.

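### Urinary retention can be reported only in patients who could void before treatment, but the visible SAP takes its percentage over all treated patients; an at-risk row should be added

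*SAP*

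**What the plan says.** **Who can contribute an event.** Protocol 9.1.2 gives urinary retention a study-specific definition and limits who may be reported: "Urinary retention should only be reported in patients who had the ability to spontaneously void between catheterizations prior to study treatment". Within that group the event is "the inability to spontaneously void for at least 24 hours, which is not in conjunction with the patient experiencing constipation".

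**Who is counted in the denominator.** Protocol 7.4: "All safety analyses will be conducted on the BOTOX-treated population". SAP 2.1: "BOTOX-treated population will include all patients that enrolled into study 191622-121 after receiving BOTOX injection in study 191622-120". Neither mentions voiding ability. SAP 6.2 then applies one rule to all preferred terms, by cycle: "The number and percentage of patients reporting TEAE in each treatment group will be tabulated by descending percentage in any group". The additional table for events up to day 84 also reports percentages of patients by preferred term and treatment group.

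**Entry.** Protocol 4.3: "patient must be regularly using CIC to empty the bladder". No visible criterion requires that the patient can also void spontaneously.

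**Other treatment of retention.** UTI has its own summaries in SAP 6.2. The visible text has none for retention. SAP 6.2.1 excludes retention from the distant-spread events because it is an expected local effect.

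**Data at hand.** According to SAP 2.3.1 the diary collects the "type of voiding episode (urinary incontinence, catheterization, or voluntary void) for each daytime episode".

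**The concern.** The numerator is restricted to patients with residual voluntary voiding, while the denominator is not. Patients who empty the bladder only by catheter are counted as event-free, although the protocol does not allow the event to be reported in them. The wording of 9.1.2 itself anticipates that such patients are enrolled.

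Two things are at stake. First, a reader asking how often a child who can still void loses that ability after injection gets a diluted answer, and cannot correct it because the number able to void is not shown. Second, SAP 6.2 presents the day-84 table as a more direct comparison of dose groups. If the share able to void differs between groups or cycles, the retention row compares different mixtures of patients.

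Protocol Section 1 names retention and UTI as the leading adverse events of the adult programme, and 9.1.2 singles out these same two for definition here. The retention row is therefore likely to be read closely.

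**Working it through.** The documents state no retention rate and no share of patients able to void, so there is no planned figure to reproduce.

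**Inputs**
- Numerator restriction: protocol 9.1.2.
- Denominator, all treated patients in the dose group and cycle: SAP 6.2 with protocol 7.4 and SAP 2.1. The SAP does not write out a denominator for retention; this is the natural reading.
- Expected number of patients: 78 (SAP 1.1.1) or 100 (protocol 7.6).
- f, the share able to void before treatment: not given. Assumed range 10% to 100%.
- Event count of 3: illustrative only.

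**Formula.** Let x be the number of patients with retention, N all treated patients and m = f × N those able to void.

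Tabulated % = x/N = f × (x/m), so at-risk % = tabulated % × 1/f.

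**Results for N = 78, 3 illustrative events, m rounded to whole patients.** The all-patient figure is 3/78 = 3.8% throughout.

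| f | 1/f | m | At-risk % | Tabulated % if at-risk incidence is 10% |
|---|---|---|---|---|
| 100% | 1 | 78 | 3/78 = 3.8% | 10% |
| 75% | 1.3 | 58 | 3/58 = 5.2% | 7.5% |
| 50% | 2 | 39 | 3/39 = 7.7% | 5% |
| 25% | 4 | 20 | 3/20 = 15.0% | 2.5% |
| 10% | 10 | 8 | 3/8 = 37.5% | 1% |

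With N = 100, 3 events read as 3.0% over all patients, and as 4.0%, 6.0%, 12.0% and 30.0% over 75, 50, 25 and 10 at-risk patients.

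**Comparison between groups (assumed values).** Suppose two dose groups have the same at-risk incidence of 10%, with f = 75% in one and 25% in the other. The tabulated rates are 0.75 × 10% = 7.5% and 0.25 × 10% = 2.5%, a threefold difference that comes only from the denominator. Conversely, at-risk rates of 5% and 15% with the same two shares both tabulate as 3.75% (0.75 × 5% and 0.25 × 15%), and the difference disappears.

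**Timing.** Protocol 9.1.2 does not say whether voiding ability must precede the first injection or each injection. If it is judged before each cycle, a patient who lost the ability after an earlier injection leaves the at-risk set. Thus f could change from cycle to cycle.

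**The case against.** The planned percentage is not wrong. Events over all treated patients is a valid proportion: the share of this catheterizing population with a reported event. The at-risk percentage answers a different question. This stands, and it is why the standard row should stay.

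The size is unknown. If every patient can void, the two percentages coincide. This also stands.

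A reader might infer several stronger things that the documents do not support:
- *That the tables will show too tight an upper confidence limit.* The visible text of SAP 6.2 plans counts and percentages for adverse events, with no intervals.
- *That no other output can give an at-risk rate.* The visible SAP goes from 6.2.1 to Section 8, and some entry criteria and safety text in the protocol are also not visible. Such a table, or an entry rule on voiding, cannot be excluded. The exclusion from the distant-spread table does not bear on this, because nothing there sets an at-risk denominator.
- *That retention is an established main risk in these patients.* The statement in protocol Section 1 concerns adults, and the dose-dependent rise in residual urine reported there was in patients not catheterizing before treatment. Everyone here catheterizes.
- *That a dose signal will be hidden or created.* Doses in the preceding study were randomized, so voiding ability in cycle 1 should be roughly balanced, apart from selection at rollover and regrouping under the weight cap. Later doses depend on response, so all later dose comparisons are already confounded, and protocol 7.3 plans no hypothesis tests. Distortion is possible, but it is not shown.

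None of this removes the mismatch between who can be counted above the line and who is counted below it.

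**Conclusion.** The point holds as a matter of interpretation and completeness. On the visible text, the retention percentage understates incidence among patients who can have the event whenever at least one treated patient could not void beforehand. The direction follows from the definitions. The factor is 1/f: 1 at f = 100%, 1.3 at 75%, 2 at 50%, 4 at 25% and 10 at 10%. The documents do not allow a choice within that range.

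The conclusion rests on two assumptions: that the general rule in SAP 6.2 governs retention, and that no text hidden from view supplies an at-risk table. The crude percentage should be described as a proportion of all treated patients, not called false. Any distortion across doses or cycles depends on f differing between them, which is plausible after cycle 1 but undocumented.

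**What to change.** In SAP 6.2, keep the standard row and add the following.

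1. **An at-risk row.** Tabulate urinary retention as n/N by cycle and dose, for the whole cycle and up to day 84, among patients able to void spontaneously before treatment, with N shown.
2. **A definition from pre-treatment information only.** Class a patient as at risk if the pre-treatment diary contains at least one voluntary void, or if a pre-treatment record of voiding ability exists and confirms it.
3. **The reference time.** State whether voiding ability is judged before the first injection or before each cycle.
4. **Events outside the set.** List separately any retention event in a patient not classed as at risk. Do not move that patient into the denominator because of the event. Patients misclassified in the same way but without an event would stay out, so the rate would be biased upward, most of all when N is small.

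The cost is a few lines of SAP text and one extra table, largely from diary data already collected. Trial conduct does not change. The percentage will look less favourable and be less precise. For example, 3/20 has an exact 95% interval of 3.2 to 37.9%, against 0.8 to 10.8% for 3/78 (my calculation; no such interval is planned). A 2-day diary is only a proxy for voiding ability, so some misclassification will remain and should be acknowledged in a footnote.

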#### 9.1.4 Severity

A clinical determination will be made of the intensity of an adverse event. The severity assessment for a clinical adverse event must be completed using the following definitions as guidelines:

Mild Awareness of sign or symptom, but easily tolerated.

Moderate Discomfort enough to cause interference with usual activity.

Severe Incapacitating with inability to work or do usual activity.

Not applicable In some cases, an adverse event may be an 'all or nothing' finding

which cannot be graded.

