# 9.1.5 Relationship to Study Drug or Study Procedure

A determination will be made of the relationship (if any) between an adverse event and the study drug or study procedure, as applicable. A causal relationship is present if a determination is made that there is a reasonable possibility that the adverse event may have been caused by the drug or study procedure.

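### SAP 6.2 selects the greatest-severity event for the causality summary too, so a milder related event can be lost behind a more severe unrelated event of the same preferred term in the same cycle

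*SAP*

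**What the plan says.** Protocol 7.4 asks for adverse event tables by relationship: "The tables will be generated by relationship to treatment as well as by primary system organ class and severity". It gives no rule for a patient who has several events under one term.

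SAP 6.2 supplies the rule. Patients with treatment-emergent events are tabulated by system organ class and preferred term, "further categorized by severity and causal relationship to the study drug and study drug injection procedure". The level of reporting is the cycle: "The incidences of TEAEs will be summarized by BOTOX treatment cycle". Where a patient has more than one event, "the patient will be counted only once for that preferred term using the greatest severity for the summarization by severity and causal relationship".

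Severity and relationship are separate judgements. Protocol 9.1.5 defines relationship, whether to drug or to procedure, as present or absent for each event: "A causal relationship is present if a determination is made that there is a reasonable possibility that the adverse event may have been caused". Protocol 9.1.4 grades severity as mild, moderate or severe, and adds an ungraded category: "In some cases, an adverse event may be an 'all or nothing' finding".

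Two other outputs in SAP 6.2 bear on the point. Related events also appear in a summary over the whole study: "study drug/study injection procedure related TEAEs, deaths and TEAEs leading to study discontinuation will be reported for the overall study period". The listings named there are limited: "separate patient listings will be generated for deaths, SAEs, and TEAEs leading to study discontinuation".

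**The concern.** The event with the greatest severity need not be the related one. If the causality table takes its relationship from the most severe event, a related event of lower severity leaves no trace in the related column for that term and cycle.

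This matters most for terms that recur. The documents expect urinary tract infection to recur: SAP 4.2 classifies prior infections as 0, 1, 2, 3 or more than 3 in six months, and SAP 6.2 plans event rates per patient-year. A cycle lasts at least 12 weeks before retreatment can be requested (Protocol 5.10.1) and can run much longer, so two or three events of one term in one cycle are plausible.

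Long-term safety is a study objective and there is no control group (Protocol 2.1 and 5.2). Investigator attribution is therefore one of the few ways to separate drug or procedure effects from background events. SAP 6.2 itself notes that time in a cycle varies. If cycle length differs by dose, the chance of repeat events, and so of loss, could differ between the dose groups being compared.

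**Working it through.** The plan states no figure on this point, so there is nothing to reproduce. The check applies the rule literally and then shows how far it can depart from a count of patients with any related event.

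**Step 1. One patient, one cycle, one preferred term.** Event A is mild and related. Event B is severe and unrelated.

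| Summary | SAP 6.2 as written | Strongest relationship for causality |
|---|---|---|
| Severity | severe = 1 | severe = 1 |
| Related | 0 | 1 |
| Not related | 1 | 0 |

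If instead A is the more severe event, both rules give related = 1. A patient with no related event is counted as not related under both. The difference therefore runs in one direction only.

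**Step 2. Two events, illustrative inputs.** All of these are assumptions; none is in the documents. The probability that an event is judged related is r = 0.3, independently between events and independently of severity. Severity is mild, moderate or severe with probability 0.6, 0.3 and 0.1.

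- At least one related: 1 − (1 − 0.3)² = 0.51.
- Tie in severity: 0.6² + 0.3² + 0.1² = 0.46, so no tie: 0.54.
- No tie: the more severe event is related with probability 0.3, contributing 0.54 × 0.3 = 0.162.
- Ties counted as related if either event is: 0.162 + 0.46 × 0.51 = 0.397.
- Ties counted as related only if both are: 0.162 + 0.46 × 0.3² = 0.203.

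The rule therefore reports between 20% and 40%, against 51% with any related event. The width of that interval comes entirely from the missing tie rule.

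**Step 3. Varying the assumptions** (60/30/10 severity split, independence kept):

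| r | Events | Any related | Rule, ties to unrelated | Rule, ties to related | Share of related patients lost |
|---|---|---|---|---|---|
| 0.1 | 2 | 19.0% | 5.9% | 14.1% | 26% to 69% |
| 0.1 | 3 | 27.1% | 5.9% | 15.9% | 41% to 78% |
| 0.3 | 2 | 51.0% | 20.3% | 39.7% | 22% to 60% |
| 0.3 | 3 | 65.7% | 19.4% | 42.7% | 35% to 71% |
| 0.5 | 2 | 75.0% | 38.5% | 61.5% | 18% to 49% |
| 0.5 | 3 | 87.5% | 36.1% | 63.9% | 27% to 59% |

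With severity split into equal thirds added, the share lost spans about 18% to 45% when ties go to related and 44% to 78% when they go to unrelated. The base is patients with two or three events under one term in one cycle, at least one of them related.

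**Step 4. Relaxing independence between events** (r = 0.3, two events, 60/30/10). With correlation 0.5 between the two judgements:

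- Both unrelated: 0.7² + 0.5 × 0.3 × 0.7 = 0.595, so any related = 0.405.
- Both related: 0.3² + 0.5 × 0.3 × 0.7 = 0.195.
- Rule: 0.162 + 0.46 × 0.195 = 0.252 to 0.162 + 0.46 × 0.405 = 0.348.

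The gap is then 40.5% against 25% to 35%. If repeat events are always rated alike, every figure is 30% and nothing is lost.

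**The case against.** The sponsor may have meant something harmless. The sentence could be shorthand for greatest severity within each relationship category, or the related table might be built by filtering to related events first. Under either, no related event disappears. This is a fair point about intent, but the text states neither, and two programmers could produce different related counts from the same data. The missing tie rule and the unranked ungraded category stand whatever was intended.

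Other outputs also limit the damage. The overall-period incidence of related events may count the patient correctly, since the once-per-term sentence does not obviously govern it. The infection summaries and rates in SAP 6.2 retain the infections regardless of cause. All-causality incidence by term and the serious-event outputs do not depend on the selection. These stand as mitigation. They do not repair the per-cycle, per-dose, per-term relationship table: no term or cycle breakdown is stated for the overall-period figure, the infection summaries carry no causality split, and the listings named in SAP 6.2 would omit a mild, non-serious related event.

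Three stronger readings are not supported:

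- A reader might infer that any severe unrelated event hides any milder related one. The rule works within a preferred term, so an event under a different term hides nothing.
- A reader might take a gap such as 51% against 30% as the bias in reported incidence. That gap would apply only to patients with repeat same-term events, and 30% presumes either no ties or a random tie-break. The share of such patients is not in the documents.
- A reader might see a conflict between protocol and SAP. Protocol 7.4 requires the tables but gives no counting rule, so there is none.

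**Conclusion.** The point holds within limits. As written, SAP 6.2 takes a patient's relationship category from the most severe event of a preferred term. Per-cycle, per-term counts of related events can then be understated but not overstated, relative to counting any related event. The effect needs at least two events of the same term in the same patient and cycle, judged differently for relationship, with an unrelated one selected.

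The effect on the final tables cannot be determined, because the frequency of repeat events and the agreement between their causality ratings are not given. The figures above illustrate the mechanism under assumed inputs. They run from no loss at all, when repeat events are always rated alike, to more than half of the affected patients when events are independent and ties go to unrelated. No hypothesis test depends on this (Protocol 7.3). It concerns how the descriptive safety tables are read.

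**What to change.** Replace the counting sentence in SAP 6.2 with:

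> For summaries by severity, the patient is counted once per preferred term at the greatest severity; for summaries by relationship, the patient is counted once per preferred term at the strongest relationship, separately for study drug and for injection procedure.

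Because relationship is present or absent under Protocol 9.1.5, this counts a patient as related if any event of the term is related, and severity ties no longer matter for causality. It is worth stating in the same place where the ungraded category ranks in the severity summary.

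The change costs one sentence and a small programming edit, and uses data already collected. Its downside is that related incidence may come out somewhat higher.
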